1.3 Patient eligibility criteria

Patient eligibility criteria are listed in Section 5 of the protocol.

1.4 Study interventions

In Stage 2 of the STREAM trial, the primary comparison being made is between Regimen C and Regimen B, with secondary comparisons between Regimen D and Regimen B. In addition, a limited number of secondary analyses will make comparisons between Regimen A and the other regimens.

Regimen A: The locally-used MDR-TB regimen in accordance with 2011 WHO MDR-TB treatment guidelines¹.

Regimen B: Regimen B forms the control regimen for the primary and secondary comparisons, and is based on the regimen described by Van Deun 2010^2 (updated results³) consisting at the start of STREAM of clofazimine, ethambutol, moxifloxacin, and pyrazinamide given for 40 weeks, supplemented by isoniazid, kanamycin, and prothionamide for the first 16 weeks; this combination is referred to as Regimen B_{mox}. With Version 8.0 of the protocol Regimen B is modified by replacement of moxifloxacin with levofloxacin (referred to as Regimen B_{lev}). Regimen B without specification of which fluoroguinolone is in the regimen

refers to either (B_{mox} or B_{lev}). With Version 10.0 of the protocol, Regimen B is further modified to replace kanamycin with amikacin in sites where:

- the national TB program has replaced kanamycin with amikacin in line with revised WHO guidance⁴ and
- amikacin is available for the trial.

Kanamycin will continue to be used until the transition takes place within each country programme.

Regimen C: Regimen C is an all-oral modified version of Regimen B, consisting of bedaquiline, clofazimine, ethambutol, levofloxacin, and pyrazinamide given for 40 weeks, supplemented by isoniazid, and prothionamide for the first 16 weeks.

Regimen D: Regimen D a shortened modified version of Regimen B, consisting of bedaquiline, clofazimine, levofloxacin, and pyrazinamide given for 28 weeks, supplemented by isoniazid, and kanamycin for the first 8 weeks.

All patients in Stage 2 of the study will be followed up to Week 132. The primary analysis will be based on data accrued to Week 76; the data accrued to the date when the last patient is projected to have reached Week 96 will be used for the secondary long-term efficacy analysis; all data accrued to Week 132 will be used in the long-term safety analysis.

1.5 **Treatment phases**

Regimen B, Regimen C, and Regimen D each consist of 2 phases; an intense phase followed by a continuation phase, as shown in Figure 1.

[figure not shown]

Figure 1: Regimen treatment phases

For patients randomised to Regimen B or Regimen C the algorithm described in Figure 2 will be used to determine when a patient can proceed from the intensive to the continuation phase.

Patients randomised to Regimen B or Regimen C will receive 40 weeks of treatment (16 weeks intensive phase plus 24 weeks continuation phase). In the event of positive (at least "scanty" on the IUATLD/WHO scale) AFB smear, the drugs in the intensive phase of these regimens may be extended by 4 weeks twice, allowing a maximum total duration of 48 weeks treatment (except for bedaquiline, which will be given for a maximum duration of 40 weeks regardless of whether the regimen is extended).

Patients randomised to Regimen D will receive 28 weeks of treatment (eight weeks intensive phase plus 20 weeks continuation phase). As Regimen D has shorter intensive phase duration than Regimen B and Regimen C, it is expected that more patients would have a smear positive result at the end of the intensive phase due to the shorter time that patients will have been on treatment to that point. Therefore, the less stringent criterion of a smear positive result of 2+ is sufficient for patients to require an extension of the intense period, i.e. patients can have a positive smear of 1+ and still advance on to the continuation phase, as opposed to Regimen B and Regimen C for which any positive smear result would result in an extension to the intensive phase. In the event of a 2+ or more positive smear, the drugs in the intensive phase of the regimen may be extended by 4 weeks twice, allowing a maximum total duration of 36 weeks treatment (Figure 3).

The procedure for transition from the intensive to the continuation phase in Regimen A will be according to local policy.

Smear results at intensive phase Proceed to continuation phase Negative Week 16 Positive Extend intensive phase by four weeks Smear results at intensive phase Proceed to continuation phase Negative Week 20 Positive Extend intensive phase by four weeks Smear results at intensive phase Proceed to continuation phase Negative Week 24 Positive Based on all evidence to date, following discussion with No Proceed to continuation phase the central clinical team, does this patient need additional treatment? Patient retreated and classified as having an unfavourable outcome

Figure 2: Transition from intensive to continuation phase for patients on Regimen B and Regimen C

Note: smear results based on regular AFB ZN or auramine staining and not FDA vital staining.

[figure not shown]

Figure 3: Transition from intensive to continuation phase for patients on Regimen D

1.6 Randomisation procedure

Patients were initially randomised to Regimen A, Regimen B, Regimen C, or Regimen D, in a ratio 1:2:2:2, respectively. From protocol version 6.3 onwards randomisation to Regimen A and/or Regimen D were restricted or stopped (Table 1).

Randomisation will be stratified by (1) site, (2) HIV status (split into three strata: HIV negative, HIV positive with CD4 count \geq 350 cells/mm³, and HIV positive with CD4 count < 350 cells/mm³).

Table 1: Randomisation according to protocol version

Protocol version	Allocation ratio	Regimens
6.2	1:2:2:2	A:B:C:D
6.3 or 7.0	1:1:1	B:C:D in countries where the local NTP adopted or has imminent plans to adopt the WHO 2016 short regimen; as for v6.0 elsewhere
8.0 onwards	1:1	B:C

All analyses will be stratified by randomisation protocol to ensure comparisons are made to concurrent controls:

- comparisons of Regimen C to Regimen B will include all participants allocated to these regimens but be stratified by a 3 level variable: v6.2 vs v6.3/7.0 vs 8.0/10.0
- comparisons of Regimen D to Regimen B will be restricted to participants randomised under protocol v6.2/6.3/7.0 and be stratified by a 2 level variable : v6.2 vs v6.3/7.0
- comparisons to Regimen A will be restricted to participants randomised under v6.2 of the protocol

Analyses of the primary endpoint will also be stratified by HIV status as defined above, unless there is insufficient data within strata. If this is the case initially the two HIV positive groups will be combined, but if there is still insufficient data within strata then stratification by randomisation protocol will be prioritised.

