#### 2.1.4 Ending randomisation to Regimen A

According to Version 7.0 of the Stage 2 protocol, patients may be randomised to Regimen A unless the participating country has adopted or has imminent plans to adopt a short MDR-TB regimen, in keeping with the WHO 2016 guidelines. This is because patients eligible for STREAM would also meet the WHO criteria for a shortened regimen and it is very unlikely that patients would accept the possibility of randomisation to a 20- to 24-month treatment regimen when under routine care they would be treated with a 9-month regimen. In addition, patients already enrolled in the trial and allocated to Regimen A would be more likely to subsequently withdraw from the trial, thus reducing the scientific value of the results.

With Version 8.0 of the protocol, randomisation to Regimen A will cease completely because several of the countries participating in STREAM have already implemented or have plans to implement a shortened regimen. As a result Regimen A would not have sufficient concurrently randomised patients for comparison and therefore continuation is considered futile. In addition, Stage 1 of

\* Following implementation of protocol Version 8.0 recruitment to Regimen A and Regimen D was discontinued and in Regimen B moxifloxacin was replaced by levofloxacin. Following implementation of protocol version 10.0, either kanamycin or amikacin will be used in Regimen B, depending on availability.

STREAM provides a good estimate of the performance of Regimen A under trial conditions. Patients already enrolled and allocated to Regimen A will continue on that treatment.

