## Stage 1 (before Stage 2 begins, or for sites only participating in Stage 1)

Patients will be randomised to Regimen A or Regimen B. Randomisation will be in a 1:2 ratio in favour of Regimen B to allow more data on efficacy and safety to be collected on this regimen. Randomisation will be stratified by (1) site, (2) HIV status for sites with high TB-HIV co-infection rates.

### Stage 2

Prior to the implementation of Version 8.0 of the protocol, in countries where the local NTP has no imminent plans to adopt a short regimen, in keeping with the WHO 2016 MDR-TB guidelines, patients will be randomised to one of four regimens, Regimen A, Regimen B or Regimen C, or Regimen D in a ratio of 1:2:2:2. In countries where the local NTP has adopted or has imminent plans to adopt a short regimen in keeping with the WHO 2016 guidelines and it has been agreed with the STREAM Trial Management Group that randomisation to Regimen A will not be offered, patients will be randomised to one of three regimens (Regimen B, Regimen C or Regimen D) in a ratio of 1:1:1 (see Section 2.1.4). When Version 8.0 of the protocol has been implemented, randomisation to Regimen D will be discontinued as will Regimen A if it has not already been discontinued.

Randomisation will be stratified by (1) site, (2) HIV status & CD4 count status (i.e. three categories: HIV-negative, HIV-positive with low CD4 count of 50 to less than 350 cells/mm^3, or HIV-positive with high CD4 count of more than or equal to 350 cells/mm^3), for all sites.

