Analyses will only include concurrently randomised patients. For example, analyses involving comparisons with Regimen A will only include data from patients who were part of the four-arm randomisation. Data from sites that only recruited to three regimens will be excluded from these comparisons, as will data from patients randomised after the change from four to three regimens in sites where this change was made. Details are provided in the Statistical Analysis Plan.

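### SAP 1.6 limits Regimen A comparisons to protocol v6.2, narrower than its own aim of concurrent controls; any four-arm patients randomised under v6.3/7.0 are dropped without a stated reason (minor)

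*SAP*

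**What the plan says.** SAP 1.6 gives its aim first: "All analyses will be stratified by randomisation protocol to ensure comparisons are made to concurrent controls". Three rules follow, all written by protocol version. C versus B uses everyone, in three version strata. D versus B uses v6.2, v6.3 and v7.0, in two strata. For Regimen A, "comparisons to Regimen A will be restricted to participants randomised under v6.2 of the protocol".

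Table 1 in the same section does not confine four-arm allocation to v6.2. Its row for v6.3 or 7.0 reads "B:C:D in countries where the local NTP adopted or has imminent plans to adopt the WHO 2016 short regimen; as for v6.0 elsewhere".

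The protocol agrees. Section 2.1.4: "According to Version 7.0 of the Stage 2 protocol, patients may be randomised to Regimen A unless the participating country has adopted" a short regimen or is about to; complete cessation comes only with v8.0. Section 6.2 (Stage 2) describes the period before v8.0. Where no adoption is imminent, "patients will be randomised to one of four regimens, Regimen A, Regimen B or Regimen C, or Regimen D in a ratio of 1:2:2:2". Where adoption has happened or is imminent, and the trial management group has agreed not to offer A, "patients will be randomised to one of three regimens (Regimen B, Regimen C or Regimen D) in a ratio of 1:1:1".

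Protocol 11.6 states the rule for these comparisons by allocation scheme: "analyses involving comparisons with Regimen A will only include data from patients who were part of the four-arm randomisation". It then excludes three-arm sites, and patients randomised after their own site moved from four arms to three, and refers to the SAP for details. SAP 7.1.4 asks for concurrent controls within sites for B–A, C–A and D–A at Week 132.

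**The concern.** Protocol version stands in for allocation scheme, and under v6.3/7.0 the two differ. A patient randomised to A under v7.0 in a non-adopting country was allocated 1:2:2:2 alongside B, C and D patients at the same site and time. That patient meets the purpose stated in SAP 1.6, the four-arm condition of Protocol 11.6 and the within-site condition of SAP 7.1.4, but fails the version filter. The matching controls are lost too.

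The comparisons at stake are secondary: SAP objectives 8 to 10 (estimated differences of B, C and D from A at Week 132), B–A mortality (SAP 7.2.2) and B–A grade 3 or greater adverse events (SAP 7.2.3, objective 13). Regimen A is small to begin with (Protocol 11.4.3 expects no more than 50), so avoidable losses are noticeable.

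A smaller gap sits beside this. SAP 7.2.2 repeats the mortality analysis for A and B together against C and D together. It does not give the levels of the randomisation-protocol factor for that contrast, or say whether the v6.2 rule applies to it.

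**Working it through.** The plan states no sample size or precision for comparisons with A, so there is no figure to reproduce. The check has three parts.

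**1. Which patients each rule keeps**

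| Randomised under | Scheme at site | Concurrent A controls? | SAP 1.6 | Four-arm rule |
|---|---|---|---|---|
| v6.2 | A:B:C:D 1:2:2:2 | yes | kept | kept |
| v6.3/7.0, non-adopting country | A:B:C:D 1:2:2:2 | yes | dropped | kept |
| v6.3/7.0, adopting country | B:C:D 1:1:1 | no | dropped | dropped |
| v8.0 onwards | B:C 1:1 | no | dropped | dropped |

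Only the second row differs. C versus B and D versus B are not affected, because B:C and B:D are 1:1 in every scheme where both arms were open.

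**2. Effect on precision of B–A**

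Inputs: A at most 50 and D about 100 (Protocol 11.4.3); A:B = 1:2; favourable 80% in both arms (rounded from the Stage 1 Week 132 figures of 79.8% and 78.8%, Protocol 2.1.1); grade 3 or greater events 45.4% on A and 48.2% on B (same section); mortality 8% in both arms (the Stage 1 figure for B in Protocol 11.4.1, assumed for A as well). The fraction f of A randomised after v6.2 is not in the documents; 0, 10% and 25% are assumptions.

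With nA = 50(1−f) and nB = 2nA, the unstratified half-width is 1.96 × sqrt[pA(1−pA)/nA + pB(1−pB)/nB]. Controls are lost in proportion, so f enters only as the factor 1/sqrt(1−f).

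Favourable, f = 0: 1.96 × sqrt(0.16/50 + 0.16/100) = 1.96 × 0.0693 = 13.6 points.

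| f | nA / nB | Factor | Favourable | Grade ≥3 AE | Mortality |
|---|---|---|---|---|---|
| 0 | 50 / 100 | 1.00 | 13.6 | 16.9 | 9.2 |
| 10% | 45 / 90 | 1.05 | 14.3 | 17.8 | 9.7 |
| 25% | 37.5 / 75 | 1.15 | 15.7 | 19.5 | 10.6 |

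The Week 132 estimator in SAP 7.1.4 is a stratum-weighted survival difference from a Cox model. Simulating it (exponential times, 20% unfavourable by Week 132, HIV strata assumed 70/15/15%, no earlier censoring) gives about 13.4 points at A = 50 and 14.1 at A = 45, so the simple formula is adequate.

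A = 50 is a ceiling. A:D is 1:2 only under four arms, so if a share s of the 100 D patients came from three-arm randomisation, A = 100(1−s)/2: 50 at s = 0 and 37.5 at s = 25%. Starting from 37.5, the favourable half-width is 15.7 at f = 0 and 18.1 at f = 25%.

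**3. A and B versus C and D, mortality**

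The ratio (A+B):(C+D) is 3:4 under four arms and 2:4 = 1:2 under three. Suppose a v6.3/7.0 stratum is half four-arm. The four-arm share is (3/14)/(3/14 + 1/6) = 56.25% of A+B and (2/7)/(2/7 + 1/3) = 46.15% of C+D, a gap of 10.1 percentage points. If mortality differs by an assumed 5 points between four-arm and three-arm countries, the spurious difference inside that stratum is 0.101 × 5 = 0.5 points.

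For the overall effect, take B = C = D = 100 before v8.0, B = C = 100 after, and Cochran-Mantel-Haenszel weights n1n2/(n1+n2):
- Half of pre-v8.0 D in the mixed stratum: weights 38.1 (mixed), 42.9 (v6.2) and 50 (v8.0 onwards). The mixed share is 29%, giving about 0.15 points.
- All of pre-v8.0 D in it: weights 76.2 and 50. The mixed share is 60%, giving about 0.3 points.

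These two scenarios imply about 37 and 23 patients on A. They cannot be combined with the A = 50 half-widths in part 2.

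**The case against.** **The protocol leaves this to the SAP.** That stands. Protocol 11.6 sets an upper limit on who may enter and sends the reader to the SAP for details. A reader might infer that SAP 1.6 contradicts Protocol 11.6 or SAP 7.1.4. It does not: the v6.2 set satisfies both. What remains is that the rule is narrower than its own purpose, with no reason given.

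**Nobody may be affected.** Also fair. A reader might infer from Table 1 that patients were in fact randomised to A after v6.2. The documents show permission only. Protocol 1.1.4 says that some countries had already implemented the short regimen and most of the rest planned to start during 2018, so the pool may be small or empty.

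**v6.2 may be shorthand for the four-arm scheme.** Table 1 does use a version number that way once, in referring back to v6.0. But the C and D rules treat v6.2 and v6.3/7.0 as separate levels, and a programmer would filter on version.

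**Later Regimen A patients may withdraw more.** Protocol 2.1.4 warns that once a short regimen is adopted, "patients already enrolled in the trial and allocated to Regimen A would be more likely to subsequently withdraw from the trial". That could be a reason for an early cut, but the SAP does not offer it. The warning covers everyone already on A, including the v6.2 patients whom the rule keeps, and the documents give no figures by version. Showing the v6.2-only result alongside lets readers judge.

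**Conclusion.** The point holds as a minor one. The v6.2 restriction is valid but narrower than needed, and it removes any four-arm patients randomised under v6.3/7.0, with their concurrent controls.

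It would be wrong to read this as bias: the rule admits no non-concurrent controls. The cost is precision only, by the factor 1/sqrt(1−f). With A at its ceiling of 50, that is an increase of 0.7 points in the favourable half-width at f = 10% and 2.1 points at f = 25%. It is nothing if f = 0. These figures rest on assumed f, a fixed 1:2 ratio and Stage 1 rates. The primary Week 76 comparison of C with B is not affected.

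On pooled mortality, a reader might infer that no strata are specified or that the result is materially distorted. Neither is supported. SAP 1.6 and 7.2.2 name randomisation protocol and HIV status as strata; only the levels for this contrast, and the reach of the v6.2 rule, are left open. The artefact is about 0.15 to 0.3 points overall, and only under the assumed 5-point gap.

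**What to change.** 1. Report Regimen A counts by protocol version. If none were randomised after v6.2, say so and leave the A comparisons as they are.
2. Otherwise define the set for comparisons with A as participants randomised while the four-arm 1:2:2:2 scheme was in force at their site (v6.2, or v6.3/7.0 at sites not yet moved to three arms), stratified by protocol version where numbers allow.
3. For A and B versus C and D mortality, keep all participants, state that the v6.2 rule does not apply, and stratify by the scheme in force at the site (four-, three- or two-arm) and HIV status.

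The cost is a few lines of SAP text and one derived variable, the scheme open at the site on the randomisation date, taken from existing records. SAP 6.1.3 shows that the current SAP postdates the primary analysis, so this should be recorded as a dated change with the v6.2-only results shown alongside. C versus B and D versus B need no change.

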2 SAMPLE SIZE

2.1 Power to demonstrate non-inferiority in the primary efficacy outcome (primary objective relating to Regimens B and C)

Stage 2 aimed to randomise at least 200 patients to each of Regimen B (B_{mox} or B_{lev}) and Regimen C. This revised sample size in protocol version 8.0 was determined based on the assumption that the proportion of patients with a favourable efficacy outcome at Week 76 is 80% for Regimen B (estimated based on preliminary Stage 1 results) and 82% for Regimen C (based on an anticipated minimum benefit in efficacy of using 40 weeks treatment with bedaquiline compared to 16 weeks treatment with kanamycin). Using a non-inferiority margin of 10% and a one-sided significance level of 2.5%, 172 evaluable patients will be required in each of the two regimens to demonstrate non-inferiority of Regimen C to Regimen B with 80% power. To account for 14% of patients excluded from the primary per protocol efficacy analysis population, a total of 400 patients will need to be enrolled across the 2 regimens.

A sample size of 400 patients enrolled to the comparison of Regimens B and C is necessary to rule out an 8% increased mortality in Regimen C compared to the 8% observed on Regimen B in the preliminary analysis of STREAM Stage 1. This will provide 80% power with a one-sided 0.025 type I error.

3 PRIMARY OUTCOME

3.1 Primary analysis Week 76 window

The Week 76 window is defined as the time period from six weeks before 76 weeks since randomisation to six weeks after 76 weeks since randomisation, i.e. from Week 70 to Week 82.

3.1.1 Extension of visit window due to the COVID-19 pandemic

The end dates of the Week 76 window will be extended for any Stage 2 patients whose Week 76 appointment is scheduled to occur during the COVID-19 pandemic and did not occur due to restrictions on movement, unacceptable risk of exposure to COVID-19 in connection with the scheduled visit, or any other reason related to the pandemic. For those patients, the Week 76 sputum samples must be taken in a window beginning six weeks prior to the scheduled visit date and ending within the Week 84 visit window i.e. within 14 weeks of the scheduled Week 76 visit date.

3.2 **Primary efficacy outcome**

The primary efficacy outcome measure is the proportion of patients with a favourable outcome (as defined below) at Week 76.

Only data from events occurring before the end of the Week 76 window will be included in the primary analysis of the primary efficacy outcome.

Culture results obtained using acidified Ogawa (Kudoh medium) will be used in the primary analysis, unless missing, when results from Löwenstein-Jensen (LJ) media will be used.

A positive culture is defined as at least one colony and a negative culture is defined as absence of growth (no colonies).

Favourable

A patient's outcome will be classified as **favourable** if their last two culture results are negative unless they have previously been classified as unfavourable. These two cultures must be taken on separate visits (on different days); the latest of which being within the Week 76 window.

Patients that don't have a culture result within the Week 76 window because they were unable to produce sputum or their sample was contaminated, will be classified as favourable if their last two cultures before the Week 76 window are negative and they have not previously been classified as unfavourable; such patients will be identified separately in tables.

Participants with no sputum sample available at Week 76 due to Covid-19 restrictions who are not otherwise classified as unfavourable will be considered unfavourable. Sensitivity analyses will reclassify these participants as i) non-assessable and excluded from the primary efficacy analysis, and ii) favourable if they meet the definition of favourable above, with the latest of the 2 negative culture results being within the Week 68 window, and unfavourable otherwise.

Unfavourable

A patient's outcome will be classified as **unfavourable** in Stage 2 if:

- 1. They are discontinued from their allocated study treatment and subsequently restarted on a different MDR-TB regimen.
- 2. Treatment is extended beyond the scheduled end of treatment for any reason other than making up days when no treatment was given (missed treatment) for a maximum of eight weeks. A maximum of 14 days of extra treatment (irrespective of reason) is acceptable before it is classified as treatment extension.
- 3. They are restarted on any MDR-TB treatment after the scheduled end of treatment, but before 76 weeks after randomisation.
- 4. They change their allocated study treatment for any reason other than the replacement of a single drug.
- 5. Bedaquiline is started where the allocated regimen did not originally contain that drug (Regimen A or B).
- 6. A second line injectable agent is started in Regimen C.
- 7. A drug from the class of nitroimidazoles (delamanid or pretomanid) or linezolid is started.
- 8. They die at any point during treatment or follow-up.
- 9. At least one of their last two culture results, from specimens taken on separate occasions, is positive.
- 10. They do not have a culture result within the Week 76 window.

Starting a single drug other than bedaquiline (in Regimen A or B) or from the class of nitroimidazoles (delamanid or pretomanid) or linezolid (in any regimen) is not considered to be a substantial change to the regimen and therefore does not result in an unfavourable outcome, providing none of the other criteria above are met.

An extension of the intensive phase of treatment in any study arm does not constitute an unfavourable outcome, as long as the extension is in accordance with the algorithms described in Figure 5 and Figure 6 in Section 1.5 for patients on Regimen B, Regimen C, and Regimen D. Similarly, the discontinuation of drugs that are not replaced does not constitute an unfavourable outcome.

These definitions of favourable and unfavourable apply to all four treatment regimens and for analyses of both the mITT, PP and mPP analysis populations.

